4.2.1 Interview Steps Delineated

- Conduct the initial 66 exit interviews and estimate the threshold for meaningful change based on results for subjects indicating any level of improvement on the NI Diary Total Score.
- Calculate the mean, standard deviation (SD), and 95% CI of the change threshold estimate based on the initial sample size of 66 subjects. If variability in the estimate is greater than the population 10-point standard deviation, an additional 5% of subjects (or 1 subject per treatment arm) will be

interviewed. The threshold will be recalculated to determine if the estimate becomes robust enough to discontinue sampling when the estimate (in whole units) does not change with 2 successive sample size increases (eg, measurement saturation).

- If measurement saturation has been reached, exit interviews will be complete. If not, subjects will continue to be interviewed at an increase of 5% of subjects per treatment arm until measurement saturation is reached.

Please see [Table 2](#) for further details.

Table 2. Cluster Sampling Design Description

Cluster	Listing Unit	Elementary Unit	Application	Methodology for Exit Interviews
Baseline severity (nocturnal voids ≥ 2)	Sites (US and Europe)	Subject: 
 • Sex (50% female) • Age (50% ≥ 65) 	
 • Inclusion of proportionate number of subjects with nocturnal voids ≥ 2 to derive meaningful change thresholds 	
 • Start with 66 subjects and increase the proportion stepwise until measurement saturation is achieved • Measurement saturation will be defined by narrowing of the 95% CIs and an effect size above 0.50 (moderate)

Abbreviations: CI, confidence interval; NI, Nocturia Impact; US, United States

4.3 Subject Recruitment

Recruitment of subjects will be purposive from the Phase 2 trial. Additional information about the trial will be provided to subjects as they are enrolled into the Phase 2 trial. Those that are willing to participate will be provided with an informed consent document to allow full disclosure about the purpose and details of the exit interview.

The clinician at the site will be asked to complete a Case Report Form ([Appendix C](#)) that includes specific requirements for subject information to be collected based on the subjects participating in the study (see [Table 2](#) for sub-sample requirements).

4.3.1 Population Characteristics

As described above, subject demographic and medical characteristics will be summarized using the techniques specified for categorical and continuous variables. These variables include:

- Age (≥ 65 and < 65 years)
- Gender
- Baseline nocturnal voids (> 2 and > 3)
- Baseline NI diary scores (mean, SD)

4.4 Interview Process

Clinical Outcomes Solutions scientific staff members will conduct all interviews with participants via telephone to allow the interview to take place as quickly as possible after exiting the trial. Interviews will be conducted in English and will take approximately 45 – 60 minutes to complete. The interview will have four parts:

1. Discussion about experience of living with nocturia and its impacts
2. Discussion about the NI Diary and what constitutes a meaningful change
3. Discussion about change in nocturnal voids and what constitutes a meaningful change
4. Completion of a satisfaction question, overall health status questions, global rating of improvement and, global impression of severity questions

The full discussion guide is provided in [Appendix D](#). Since the discussion guide is complex, mock interviews will be conducted with the interviewers to standardize the way in which it is implemented.

The telephone interviews will be recorded and a copy of the audio-file will be transmitted to a transcription company using 128-bit SSL encryption. Files are only visible to the professionals who have signed strict confidentiality agreements. A random review of transcripts vs. audio-file will be conducted by COS prior to any analysis taking place to ensure accuracy of transcription. Once the transcriptions are approved the transcription company will destroy the audio-files.

4.4.1 Payment

Upon completion of the pre-interview study documents and subject interviews, each subject will be paid \$100 via an electronic gift certificate for his/her participation.

5 Analysis

5.1 General Overview

All data processing and analyses for the qualitative interviews will be performed using ATLAS.ti v7.0. For the quantitative analyses, Statistical Analysis Software will be used.

5.2 Qualitative Data

All interview data will be audio-recorded, transcribed, and entered into ATLAS.ti v7.0, a software package which is designed to facilitate the storage, coding, and analysis of qualitative data. This program allows the researcher to code data at different levels of analysis and search for coded data using Boolean operators. The thematic coding scheme will undergo several iterations as the research team codes the preliminary data. Preliminary searches of the coded text will be conducted during and after the initial coding of the data to discover patterns in the data. Initial coded material will be coded into broader core categories and analyzed using thematic analysis. Qualitative data will be analyzed by the outcomes research team executing the study (Clinical Outcomes Solutions) to understand qualitatively what a meaningful change is on the NI Diary.

5.3 Quantitative Data

Data produced from the exit interviews will include improvement in nocturnal voids as well as levels of improvement and severity on items and domains on the NI Diary. Quantitative responses on the prospective and retrospective perceptions of improvement will be included in this evaluation, with the intent to code these responses for triangulation to the clinical trial results. As such, the following variables will be generated from the exit interviews:

- Subject exit interview data at Week 12, including the following:
 - Satisfaction will be evaluated using two methods to understand the distribution of the concept of satisfaction in this population and the relationship with nocturnal void frequency improvement.
 - Comparison of subjects stratified by the absolute response to the “Patient’s Global Impression of Improvement” (PGI-I) item.
 - Comparison of subjects who indicated that they are “very satisfied” or “somewhat satisfied” with improvement with those who indicate that they are “somewhat dissatisfied” or “very dissatisfied.”
 - PGI-I comparison between subjects who indicated that they feel “a great deal better,” “much better,” or “a little better” to those who indicated that they feel “a little worse,” “much worse,” or “a great deal worse.”
 - Patient’s Global Impression of Severity (PGI-S comparison between subjects who indicated that they are experiencing “none,” “mild,” “moderate,” and “severe” symptoms).

For perceived improvement in nocturnal voids, subjects will be categorized by change from “no” to “yes” from Baseline to Week 12. For subject interviews, which will be conducted between Weeks 12 and 14, subjects will be categorized by reported improvement as well as satisfaction with improvement in nocturnal void frequency.

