4.2 Sample Size Requirement and Cluster Sampling Design

The primary goal of the exit interview is to estimate meaningful change thresholds for the NI diary within this randomized subject population from the Phase 2 proof-of-concept trial (1:1:1:1:1 ratio; FE201836 versus desmopressin versus placebo). For each treatment arm, subjects who demonstrate improvement in the NI Diary scores from Baseline to End of Treatment will be evaluated using a paired-sample t-test. This sample size calculation is based on NI diary parameters and is a mixed methods design (eg, qualitative and quantitative evidence) in which the equivalence of paired means is tested with significance (alpha) set at 0.05, a correlation of 0.40 between assessments, a combined standard deviation of 10 (95% confidence interval [CI] lower bound equal to 10 and upper bound equal to 15), and minimal difference thresholds estimated from previous research of 8.28 and 10.30 point improvement (based on the 0 – 100 transformation). See [Table 1](#) for further details.

Table 1. Sample Size Requirement for Paired t-test of Mean Difference

Mean Improvement Level on the NI Diary Total	Standard Deviation	Actual Power	Sample Requirement per Treatment Arm	Total Subjects
8.28	10	0.807	16 subjects	96 subjects
10.30	10	0.802	11 subjects	66 subjects

Abbreviations: NI = Nocturia Impact

The above power calculation defines the size of the initial set of exit interviews and the *minimum number of subjects* who will be exit interviewed. On the basis of this sample, the change threshold is estimated for defining meaningful change. Next, the robustness of the threshold estimate to increases in sample size using the steps described below is tested). Based on the results, it will be decided whether or not to conduct additional interviews. A “robust” threshold estimate is defined as one that varies < 1 with the addition of the results of additional interviews.

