5.3.1 Score

The NI Diary Total Score is a raw score valuation ranging between 0 and 44. The current scoring algorithm presents a score transformation from the raw score range to a standardized 0 to 100 scale. Subjects will be presented with the items on the raw score range for this exercise. Within the context of this evaluation, to avoid confusion by the subjects, meaningful change thresholds will be described in raw change score units of -44 to +44 and later transformed to the -100 to +100 by the Ferring statistical programming team.

Nocturnal voids are the subject reported count of getting up during the night to void.

6 Compliance with Good Clinical Practice and Ethical Considerations

This study will be conducted in compliance with Good Clinical Practice, including International Conference on Harmonisation Guidelines and consistent with the most recent version of the Declaration of Helsinki. In addition, all applicable local laws and regulatory requirements relevant to the use of therapeutic agents will be adhered to.

The exit interviews will be conducted by experienced staff from Clinical Outcomes Solutions with specific training in conducting qualitative interviews.

If a subject reports an experience that would result in documenting a spontaneously reported adverse event, the study site will use their own standards to document the event. The physician will include the event in the case report form and send it to Clinical Outcomes Solutions within 24 hours.

All COS employees involved in the interviews or analysis of the data will be provided with specific training on reporting of adverse events, which will be provided by Ferring Pharmaceuticals.

7 Confidentiality

All personal study data collected and processed for the purposes of this study will be managed by Clinical Outcomes Solutions with adequate precautions to ensure the confidentiality of the data, and in accordance with applicable national and/or local laws and regulations on personal data protection.

The interviewers will not solicit identifying information that will link any recording to a specific subject. Names will not be transcribed, so the transcripts will remain completely anonymous. If identifying information is inadvertently verbalized during the course of the interview, the Clinical Outcomes Solutions research staff will redact the audio in the transcript. The summary report will not identify subjects by name.

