Appendix B. Nocturnal Voids

Voiding diary

1. Do you have any voiding event to report?
 YES
 NO
2. When did the voiding event take place?
----- (format in HH:MM AM/PM)

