Part 4: Rating of change on the patient global assessment of change and patient global impression of severity (5 minutes).

Introduction by interviewer: *So in this final section, I'd like to get your responses to a few other questions that ask you about your overall impression of how your nocturia has been and how it may have changed. I will read the questions and response options to you and ask that you select the response that best reflects your experience.*

13. Overall, how satisfied are you with how the study medication relieved your nocturia?

- a. Choose from: "Very satisfied," "Satisfied," "Somewhat satisfied," "Neither satisfied nor dissatisfied," "Dissatisfied," "Somewhat dissatisfied," or "Very dissatisfied"
- b. Why did you select that response?
- c. What were you thinking about to make you select X?

14. Thinking back over the course of the clinical trial, would you say your overall health status was?

- a. Choose from: "Very much improved," "Much improved," "Minimally improved," "No change," "Minimally worse," "Much worse," or "Very much worse"
- b. Why did you select that response?
- c. What were you thinking about to make you select X?

15. Check the one number that best describes how your night time urination is now (based on the past 24 hours) (PGI-S)

- a. None
- b. Mild
- c. Moderate
- d. Severe

16. Check the one number that best describes how your night time urination is now, compared with how it was before you began taking medication in this study. (PGI-I Revised)

- a. Very much better
- b. Much better
- c. A little better
- d. No change
- e. A little worse
- f. Much worse
- g. Very much worse

That is the end of the interview today. Do you have any final questions? Thank you so much for taking part today and spending time with me in answering these questions.

Appendix 2

Statistical Design and Operating Characteristics

Trial Code: 000233

**Randomized Dose-Response Trial Investigating 6 Different Oral Doses of
FE 201836 for the Treatment of Nocturia due to Nocturnal Polyuria in Adults**

*Prepared for Ferring
By Berry Consultants, LLC
December 16, 2016*

1 Introduction

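### Exit interview: the satisfaction comparison in Appendix 1 leaves the answers 'Satisfied' and 'Dissatisfied' in no group, and three related definitions need to be pinned down

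*Protocol*

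**What the plan says.** All of this is in Appendix 1 of the Protocol, the exit-interview protocol.

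- **Satisfaction.** Section 5.3 (Quantitative Data) evaluates satisfaction by two methods. One stratifies by the PGI-I answer. The other compares *very satisfied* or *somewhat satisfied* with *somewhat dissatisfied* or *very dissatisfied*. The answers come from Question 13 in Part 4 of the discussion guide: "Overall, how satisfied are you with how the study medication relieved your nocturia".
- **PGI-I.** Section 5.3 groups subjects using *a great deal better* and *a great deal worse* as the outer categories. Question 16, and Section 7.1.1.3.1 of the main Protocol, use *Very much better* and *Very much worse*.
- **Voids.** Section 5.3 adds: "For perceived improvement in nocturnal voids, subjects will be categorized by change from" no to yes, from Baseline to Week 12. It names no question.
- **Expansion of the sample.** Section 4.2.1 adds interviews on this condition: "If variability in the estimate is greater than the population 10-point standard deviation". It gives no scale. Section 5.3.1 says that "meaningful change thresholds will be described in raw change score units of -44 to +44" and that they are transformed to the 100-point scale later.

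**The concern.** The answer groups are fixed in one place and the answers are collected in another, and the two lists differ. If an analyst programs Section 5.3 literally, a subject who says plainly *Satisfied* is left out, while one who says *Somewhat satisfied* is counted. If the analyst repairs this on the day, the grouping is chosen with the answers in view.

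This matters because Section 1 of Appendix 1 says that the FDA asked for the interviews, and that the sponsor wants the NI Diary as a co-primary endpoint in registrational studies. Section 10.3.1.1 of the Protocol takes subjects' perceptions from the interviews into the anchor-based validation. Evidence for a meaningful-change threshold is weaker if its groupings can be settled afterwards. The void category and the expansion trigger raise the same difficulty: each can be applied in more than one way.

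**Working it through.** **1. Satisfaction: answers offered against answers grouped**

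| Question 13 answer, in printed order | Group in Section 5.3 |
|---|---|
| Very satisfied | satisfied |
| Satisfied | none |
| Somewhat satisfied | satisfied |
| Neither satisfied nor dissatisfied | none |
| Dissatisfied | none |
| Somewhat dissatisfied | dissatisfied |
| Very dissatisfied | dissatisfied |

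Four of seven answers are grouped. Of the three left out, two are substantive. This is not a deliberate contrast of extremes, because both *somewhat* answers are kept.

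The documents give no distribution of answers, so the number of subjects lost is unknown; logically it lies between 0 and 66. If answers were spread evenly (an assumption, for illustration only), it would be 66 × 2/7 = 18.9, or about 19 subjects, not counting the neutral answer.

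**2. PGI-I labels.** Section 5.3 lists three better and three worse categories. Four labels match Question 16 and the two outer ones do not. In order, the six categories map one to one.

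**3. Void category.** The interview takes place once, within two weeks of trial exit (Section 4.1), so no baseline interview answer exists. The possible sources are:

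- Question 5a, which asks whether nocturia got better compared with before the trial.
- Questions 3c and 1c, which ask for the typical number of night-time voids before the trial and now.
- The diary prompt in Appendix B of Appendix 1, "Do you have any voiding event to report", which opens an entry and does not ask about improvement.

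Section 5.3 points to none of them.

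**4. Scale of the 10-point SD.** Inputs from Section 4.2 are "significance (alpha) set at 0.05", "a correlation of 0.40 between assessments" and "a combined standard deviation of 10", with improvements of 8.28 and 10.30 points stated to be on the 0-100 scale. The check first reproduces Table 1, using exact noncentral-t power for a paired t-test. Sidedness is not stated; two-sided reproduces the table.

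- SD of the difference = 10 × √(2 × (1 − 0.40)) = 10.954.
- n = 16, improvement 8.28: power 0.8066 (Table 1: 0.807).
- n = 11, improvement 10.30: power 0.8021 (Table 1: 0.802).
- Six arms: 16 × 6 = 96 and 11 × 6 = 66, as in the table.

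The table reproduces only with the SD in the same units as 8.28 and 10.30. Had the 10 been a raw-score SD (22.7 on 0-100), the powers would be 0.238 and 0.237. The planning SD is therefore a 0-100 figure.

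Conversion, with a raw range of 0 to 44:

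- 10 on 0-100 = 10 × 44/100 = 4.4 raw points.
- 10 raw points = 10 × 100/44 = 22.7 on 0-100.
- Ratio = 22.7/10 = 2.27.

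If the trigger is applied after transformation there is no error. If it is applied to the raw values in which thresholds are elicited, it is 2.27 times looser than the planning SD.

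**The case against.** The best defence is that little hangs on the satisfaction groups. They are one of two methods meant to describe satisfaction and its relation to void frequency, and the other method uses the full PGI-I answer. NI Diary thresholds are elicited directly in Questions 8 to 11, and the PGI-I and PGI-S anchor analyses are in a separate psychometric plan that is not public. It is therefore not shown that these groups are the anchors for the threshold. That limits the importance of the point, but it does not make the rule in Section 5.3 agree with Question 13.

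A reader might also infer three stronger things, none of which the documents support.

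- **That the void-improvement group must be empty.** This ties the no-to-yes change to the diary prompt. On that reading, with a mean of at least two nocturnal voids required at Visit 4, going from no to yes would mean worsening and the group would be nearly empty. The text never makes that link, and Question 5a is a more natural source. What stands is that the item and its baseline are not named.
- **That the trigger is on the wrong scale, or will hardly ever fire.** Section 4.2.1 names no scale, and Section 5.3.1 gives avoiding confusion among subjects as the reason for raw units. No SD of elicited thresholds is given, so how often the trigger fires cannot be calculated. It is also not the only check: Sections 4.2 and 4.2.1 add robustness and saturation rules.
- **That the PGI-I wording loses the strongest responders.** The categories correspond in order, so this is editorial.

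**Conclusion.** The satisfaction comparison is wrong as written. Two substantive answers out of seven, and the neutral one, have no group. This follows from the text alone and needs no assumption; the number of subjects affected does need one.

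The other three items are clarifications. The PGI-I labels differ in wording only. The void category cannot be programmed until its item and baseline source are named. The trigger is 2.27 times too loose on one reading and correct on the other, so its scale has to be stated. The sample-size figures in Table 1 are right.

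None of this affects the primary endpoint, the dose-response analysis, randomisation or safety. It should be corrected because the interviews are meant to support a regulatory threshold and the correction is cheap.

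**What to change.** Change Appendix 1 as follows, before the interview answers are analysed:

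1. **Section 5.3, satisfaction.** Compare *Very satisfied*, *Satisfied* and *Somewhat satisfied* with *Somewhat dissatisfied*, *Dissatisfied* and *Very dissatisfied*. State how the neutral answer is handled.
2. **Section 5.3, PGI-I.** Use the labels of Question 16.
3. **Section 5.3, voids.** Name the item and the baseline source, for example Question 5a, or Question 3c against Question 1c. Measured diary reduction should not replace perceived improvement: it would lose the subject's perception and group subjects by the very quantity whose meaningful change is sought.
4. **Section 4.2.1, trigger.** State that the 10-point SD is on the 0-100 scale, equal to 4.4 raw points.

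The cost is wording. If the trigger would otherwise have been applied to raw values, a few more interviews may follow under the existing stepwise rule.

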5.3.1 Score

The NI Diary Total Score is a raw score valuation ranging between 0 and 44. The current scoring algorithm presents a score transformation from the raw score range to a standardized 0 to 100 scale. Subjects will be presented with the items on the raw score range for this exercise. Within the context of this evaluation, to avoid confusion by the subjects, meaningful change thresholds will be described in raw change score units of -44 to +44 and later transformed to the -100 to +100 by the Ferring statistical programming team.

Nocturnal voids are the subject reported count of getting up during the night to void.

6 Compliance with Good Clinical Practice and Ethical Considerations

This study will be conducted in compliance with Good Clinical Practice, including International Conference on Harmonisation Guidelines and consistent with the most recent version of the Declaration of Helsinki. In addition, all applicable local laws and regulatory requirements relevant to the use of therapeutic agents will be adhered to.

The exit interviews will be conducted by experienced staff from Clinical Outcomes Solutions with specific training in conducting qualitative interviews.

If a subject reports an experience that would result in documenting a spontaneously reported adverse event, the study site will use their own standards to document the event. The physician will include the event in the case report form and send it to Clinical Outcomes Solutions within 24 hours.

All COS employees involved in the interviews or analysis of the data will be provided with specific training on reporting of adverse events, which will be provided by Ferring Pharmaceuticals.

7 Confidentiality

All personal study data collected and processed for the purposes of this study will be managed by Clinical Outcomes Solutions with adequate precautions to ensure the confidentiality of the data, and in accordance with applicable national and/or local laws and regulations on personal data protection.

The interviewers will not solicit identifying information that will link any recording to a specific subject. Names will not be transcribed, so the transcripts will remain completely anonymous. If identifying information is inadvertently verbalized during the course of the interview, the Clinical Outcomes Solutions research staff will redact the audio in the transcript. The summary report will not identify subjects by name.

All study-related documentation, including audio recordings, will be held in a secure location during study execution and analysis before being transferred to Ferring's secure servers upon study completion. The audio-recordings will be archived on the COS server after 6-months and will be retained for 7 years.

No information collected during this study will be used outside of the context of the study (ie, commercial purpose) without additional written consent from the subject.

Auditors and other authorized agents of the respective Institutional Review Board, the FDA, COS, and the Sponsor will be granted direct access to the subjects' original interview and other study-related data for verification of study procedures and/or data, without violating the confidentiality of the subjects, to the extent permitted by the law and regulations. If requested, transcripts will be provided to the site investigator relating only to his or her specific patients.

In any presentations of the results of this study at meetings or in publications, the subjects' identities will remain confidential.

8 Communication and Publication of Results

The sponsor shall retain ownership of all case report forms, data analyses, and reports which result from this study.

All information obtained from the study will be regarded as confidential, until appropriate analysis and review by the sponsor are completed. The results of the study may be published or presented after the review by and in consultation and agreement with the sponsor, and such that confidential or proprietary information is not disclosed.

The Sponsor abides by the Uniform Requirements for Manuscripts Submitted to Biomedical Journals: Ethical Considerations in the Conduct and Reporting of Research; Authorship and Contributorship statement published by the International Committee of Medical Journal Editors (ICMJE).

9 Financial Disclosure

This study is funded by Ferring Pharmaceuticals.

10 Reference List

- (1) Levy, Paul S., and Stanley Lemeshow. Sampling of populations: methods and applications. John Wiley & Sons, 2013.

